3.3. Computing Environment

All statistical analyses will be performed using SAS version 9.4, unless otherwise noted. PK parameters will be derived using Phoenix WinNonlin version 8.0 or higher. Medical history and AEs will be coded using Medical Dictionary for Regulatory Affairs (MedDRA) version 20.1. Concomitant medications will be coded using the World Health Organization (WHO) Drug Dictionary version 20170901 (Enhanced) Format B3.

3.4. Baseline Definitions

For all analyses, baseline will be defined as the most recent measurement prior to the first administration of study drug.

3.5. Methods of Pooling Data

Data will be pooled across study sites within each treatment group (ELX-02 or placebo). Data will be pooled across cohorts for the placebo group.

3.6. Adjustments for Covariates

No formal statistical analyses that adjust for possible covariate effects are planned.

3.7. Multiple Comparisons/Multiplicity

Analyses will not be adjusted for multiple comparisons for this early phase study in healthy subjects with a primary objective of assessing safety, tolerability, and PK.

3.8. Subpopulations

No analyses of subject subgroups are planned.

3.9. Withdrawals, Dropouts, Lost to Follow-up

Subjects discontinued or withdrawn from the study after receiving ≤ 6 doses may be replaced upon request from the Sponsor.

3.10. Missing, Unused, and Spurious Data

In general, there will be no substitutions made to accommodate missing data points, other than described in this section. All data recorded on the eCRF will be included in data listings.

When tabulating AE data, partial dates will be handled as follows. If the day of the month is missing, the onset day will be set to the first day of the month unless it is the same month and year as study treatment. In this case, in order to conservatively report the event as treatment-emergent, the onset date will be assumed to be the date of first dose. If the onset day and month are both missing, the day and month will be assumed to be January 1, unless the event occurred in the same year as the study treatment. In this case, the event onset will be coded to the date of first dose in order to conservatively report the event as treatment-emergent. A missing onset date will be coded as the date of first dose. If the resulting onset date is after a reported date of resolution, the onset date will be set equal to the date of resolution. Imputation of partial dates is used only to determine whether an event is treatment-emergent; data listings will present the partial date as recorded in the eCRF.

Missing AE severities will not be imputed and will be considered missing in any tabulations of AE severity. When relation of AE to the study drug is missing, the AE will be considered “related” to study drug.

When tabulating concomitant medications, if an end date is missing or the medication is ongoing at the time of first dose, the medication will be considered concomitant.

All final PK parameters will be calculated based on actual time from dose. Interim PK parameters may be calculated based upon scheduled time if actual time data are not yet available.

3.11. Visit Windows

It is expected that all visits should occur according to the protocol schedule. All data will be tabulated per the nominal visit as recorded in the eCRF even if the assessment is outside of the visit window. In data listings, the relative day of all dates will be presented (see [Section 3.2](#)).

3.12. Interim Analyses

No formal interim analyses are planned for this study. Interim blinded PK analyses are planned after each cohort from Cohort 1 through Cohort 6. Safety data will be assessed by the DSMB and AVDSMB in a blinded manner at the end of each cohort up to Cohort 6.

4. STUDY ANALYSES

4.1. Subject Disposition

Subject disposition will be tabulated and will include the number of subjects randomized to each treatment (ELX-02 or placebo), the number dosed with each treatment, and the number in each analysis population by treatment and dose and separately by concentration. The frequency and percentage of subjects who prematurely discontinue from the study, along with the primary reason for discontinuation, will also be summarized.

A by-subject data listing of study completion information including the primary reason for premature discontinuation will be presented by cohort.

4.2. Demographics and Baseline Characteristics

Demographics and baseline characteristics will be summarized and presented by treatment and dose and separately by concentration. The number and percentage of subjects in each race and sex will be tabulated. Age, baseline height, baseline weight, and body mass index (BMI) will be summarized using descriptive statistics (number of subjects, mean, SD, median, minimum, and maximum). Medical history will also be tabulated.

Demographic and baseline characteristics including alcohol and stimulating beverage consumption, tobacco use, UDS, and serology (HIV, HBsAg, HCVAb) for each subject will be provided in data listings by cohort.

4.3. Pharmacokinetic Evaluations

Cohorts 1-6 blinded interim PK analyses for dose escalation recommendations by the DSMB and the AVDSMB will be the responsibility of SGS. Derivation of PK parameters for Cohorts 1-7 final analyses will be the responsibility of Early Phase QCD Team, Parexel International. For Cohorts 1-6 blinded interim analysis, the clinical team will remain blinded in that only summary tables and figures generated by the SGS team will be shared with the DSMB and the AVDSMB and no subject level data will be shared with the study team. Pharmacokinetic parameters will be calculated by noncompartmental analysis methods from the concentration-time data using Phoenix® *WinNonlin*® version 8.0 or higher.

Generation of PK tables, listings, and figures (TLFs) for the final clinical report will be the responsibility of Early Phase Biostatistics team, Parexel International.

Pharmacokinetic parameters will be generated using the PK population.

4.3.1. PK Concentrations and Parameters

4.3.1.1. Plasma PK Concentrations

Blood samples to determine ELX-02 concentrations in plasma will be drawn on Day 1 and Day 29 at the following nominal time points:

- Predose, 15 min (\pm 2 min), 30 min (\pm 5 min), 45 min (\pm 5 min), 1h (\pm 5 min), 3h (\pm 15 min), 6h (\pm 15 min), 12h (\pm 30 min), 24h (\pm 1h), 36h (\pm 1h), 48h (\pm 1h), 72h (\pm 1h).

and on Days 4, 8, 11, 15, 18 and 22 at the following nominal timepoints:

- Predose and 1h postdose (\pm 5 min).

4.3.1.2. Plasma PK Parameters

All final PK parameters will be calculated based on actual time from dose. Interim PK

parameters may be calculated based upon scheduled time if actual time data are not yet available. All values below the lower limit of quantification (BLQ) predose and in the absorption phase prior to the first quantifiable concentration will be substituted by zeros. All BLQ values occurring after the first quantifiable concentration will be treated as missing when calculating PK parameters.

The following plasma PK parameters will be determined for ELX-02, as appropriate, according to the definitions and methods of calculation below:

- C_{\max} : Maximum plasma concentration directly obtained from the experimental data of plasma concentration vs time curves, without interpolation (Day 1 and Day 29).
- t_{\max} : Time corresponding to maximum plasma concentration, directly obtained from the experimental data of plasma concentration vs time curves, without interpolation (Day 1 and Day 29).
- AUC_t : Area under the plasma concentration-time curve calculated from time of administration to the last quantifiable concentration, computed using the linear trapezoidal rule (Day 1 and Day 29).
- AUC_{24h} : Area under the plasma concentration-time curve calculated from time of administration to time 24h, computed using the linear trapezoidal rule (Day 1 and Day 29).
- AUC_{48h} : Area under the plasma concentration-time curve calculated from time of administration to time 48h computed using the linear trapezoidal rule (Day 1 and Day 29).
- AUC_{72h} : Area under the plasma concentration-time curve calculated from time of administration to time 72h, computed using the linear trapezoidal rule (Day 1 and Day 29).
- $\%AUC_{\text{extrap}}$: Percent AUC extrapolated to infinity from last observed non-BLQ concentration.
- AUC_{inf} : The area under the plasma concentration-time curve extrapolated to infinity, calculated as $AUC_t + C_{\text{last}} / \lambda_z$, where C_{last} is the last concentration above the lower limit of quantification (LLOQ) (Day 1 and Day 29). If $\%AUC_{\text{extrap}}$ is greater than 20%, the AUC value will be flagged in TLFs, footnoted, and not included in the calculation of summary statistics.
- C_{0h} : Plasma concentration observed at predose at each dosing
- C_{1h} : Plasma concentration observed at 1h postdose at each dosing.
- C_{last} : Last observed non-BLQ concentration.
- T_{last} : Time from dose when C_{last} occurs.
- $t_{1/2}$: Apparent elimination half-life associated with the terminal rate constant (λ_z), calculated as $\ln 2 / \lambda_z$ (Day 1 and Day 29).
- λ_z : Terminal elimination rate constant is calculated using clearance (CL/F) and volume of distribution (V_d/F) ($\lambda_z = (CL/F)/V$).
- V_d/F : Apparent volume of distribution (Day 1 and Day 29). V_d/F (or V_z) will be calculated based on terminal phase using the equation “Dose/ $\lambda_z \cdot AUC_{\text{inf}}$ ”, uncorrected

for fraction absorbed.

- CL/F: Apparent plasma clearance, uncorrected for fraction absorbed (Day 1 and Day 29).
- Rac_(AUC): Accumulation ratio, calculated as AUC_{72h} Day29/AUC_{72h} Day 1.
- Rac_(C_{max}): Accumulation ratio, calculated as C_{max} Day29/C_{max} Day 1.

Additional pharmacokinetic parameters may be calculated as appropriate.

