#### 1.1.2. ELX-02

[figure not shown]
ELX-02 is a [REDACTED] drug, containing an aminoglycoside-based scaffold [6'-(R)-Methyl-5-O-(5-amino-5,6-dideoxy- $\alpha$ -L-talofuranosyl)-paromamine sulfate]. Its chemical structure is shown in Figure 1:

**Figure 1:** Chemical Structure of ELX-02

ELX-02 is a designer aminoglycoside with unique pharmacological properties.

Like classical aminoglycosides, ELX-02 has poor oral bioavailability (Investigators' Brochure) but rapid parenteral (subcutaneous [SC], intravenous [IV]) absorption, reaches peak plasma concentrations within 30-60 minutes (min) after parenteral administration, has poor protein binding, has facilitated penetration in the renal cortex and low penetration into pharmacologically privileged compartments such as the central nervous system (CNS) and cochlea, is not metabolized, and is excreted unchanged by the kidney via glomerular filtration in direct proportion to creatinine clearance, and has concentration dependent activity whereby clearance depends on renal function and volume of distribution depends on weight. More details can be found in the Investigators' Brochure.

The pharmacokinetic profile of ELX-02 in plasma in animals and humans shows dose proportionality and follows classic multi-exponential decay with a rapid and large elimination phase and a slower and low distribution phase.

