#### ***Pharmacokinetics***

ELX-02 given SC was rapidly absorbed with a median time to maximum concentration ( $t_{max}$ ) of about 0.5-1.0h.  $AUC_{0-\infty}$  changed linearly with ELX-02 dose (24-fold increase for a 25-fold dose increase) and  $C_{max}$  changed in a quasi proportional way with ELX-02 dose as significant Dose effects were seen (17-fold increase for a 25-fold increase). The apparent terminal half-life was 2 to 4h in the dose range tested (0.3 mg/kg to 7.5 mg./kg).

Plasma concentration profiles were linearly and proportionally related to the dose administered. ELX-02 had a rapid elimination phase and a slower distribution phase. ELX-02 was excreted and recovered almost quantitatively in the urine during the first 12 hours.

[figure not shown]
[figure not shown]

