#### Postdose

- After dosing, subjects will remain confined to bed for four hours (except when required to void). They will then be allowed to move freely within the ward but must refrain from strenuous physical activity for the duration of the study.
- Blood samples for PK will be collected at 15 min, 30 min, 45 min, 1h, 3h, 6h, and 12h postdose (Section 7.4).
- Vital signs (supine BP, HR, RR, and oral temperature) will be measured at 30 min, 45 min, 1h, 3h, and 12h postdose after 5 minutes in a supine position.
- Brief physical examination at 6h postdose.
- Blood and urine safety test at 6h postdose.
- Urine collection for PK during 0-12h hourly UC (each void collected separately) and 12-24h postdose, 6h intervals UC (cumulative collection 12-18h, and 18-24h postdose).
- Urine samples for renal injury biomarkers and creatinine (from the last void of the 0-12h collection) (Section 7.5.1).
- 12-lead ECG recording at 3h, 6h, and 12h postdose taken after 5 minutes in a supine position.
- Assessment of local reaction of injection site(s) 45 min, 6h, and 12h postdose (Section 7.3.7).
- Blood sampling for retention at 3h postdose.
- AEs assessment and change in concomitant medications.
- Meals will be served.

The study staff will encourage the subjects to drink at least one glass (approximately 250 mL) of fluids every hour up to 10h after dosing.

#### Day 2

- Vital signs (after 5 minutes in a supine position), BP, HR, RR, and oral temperature 24h).
- 12-lead ECG (24h) taken after 5 minutes in a supine position.

- Assessment of local injection(s) reaction (24h).

Blood sample collection:

- Safety lab tests (24h)
- PK (24h and 36h)
- Blood sampling for housekeeping proteins (24h).
- Urine collection :
  - Urinalysis (24h)
  - Urine PK, 12h intervals (cumulative 24h-36h and 36-48h collection)
  - Renal injury biomarkers and creatinine (24h and 36h urine void)
- AEs assessment and change in concomitant medications.

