1. INFORMATION FROM THE STUDY PROTOCOL

1.1. Introduction and Objectives

1.1.1. Introduction

ELX-02, characterized as a eukaryotic ribosomal selective glycoside (ERSG), is a small molecule, new chemical entity being developed by Eloxx Pharmaceuticals for the treatment of genetic diseases caused by nonsense mutations. Nonsense mutations generating premature termination codons account for approximately one third of all genetic diseases. Nonsense mutations are a genetic mutation in a deoxyribonucleic acid (DNA) sequence that results in a shorter, unfinished protein product. Consequently, most nonsense mutations result in nonfunctional proteins (Mendell, 2001; Keeling, 2006). Examples of genetic diseases where nonsense mutations are part of their phenotype include Rett syndrome, Mucopolysaccharidosis type I (Hurler syndrome), Duchenne muscular dystrophy, and cystic fibrosis.

Across a series of pharmacology studies, the translational read-through capabilities of ELX-02 have been tested in in vitro cell models and in vivo animal models. ELX-02 induced expression of functional proteins with pharmacodynamic and behavioral effects with a satisfactory window of safety in several cellular and animal models of genetic disease caused by nonsense mutations, including, cystic fibrosis (CF) and cystinosis. More information on ELX-02 can be found in the Investigator's Brochure.

Eloxx Pharmaceuticals has completed two Phase 1a, single-center, randomized, double-blinded placebo-controlled single ascending dose studies in healthy human subjects. After single subcutaneous (SC) administration, ELX-02 was generally well tolerated at doses ranging from 0.3 to 7.5 mg/kg without severe or serious drug-related adverse events (AEs). The mean terminal apparent half-life ranged between 2 and 8 hours. AUC_{inf} showed dose linearity and C_{max} approximate proportionality.

This multicenter study was initiated to assess the safety, tolerability and pharmacokinetics (PK) of ELX-02 in healthy human subjects receiving multiple escalating doses (ranging from 0.1 to 5.0 mg/kg) via SC injection(s) in a randomized, double-blinded, placebo-controlled design.

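### The linear trapezoidal rule over a sparsely sampled decline overstates AUC, by about 7-8% at half-lives of 2-4 h and about 4% at 8 h, and understates CL/F, Vd/F and renal clearance to match

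*SAP*

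**What the plan says.** SAP 4.3.1.2 defines AUCt, AUC24h, AUC48h and AUC72h as "computed using the linear trapezoidal rule". Protocol 7.4.4 has the same rule. Neither has a separate rule for the declining part of the curve. AUCinf is AUCt plus Clast/λz, so it carries the same error. Vd/F is Dose/(λz × AUCinf) (SAP 4.3.1.2), and renal clearance is Ae72h divided by AUC72h (SAP 4.3.1.4). No formula is given for CL/F; I take Dose/AUCinf.

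Protocol 7.1 sets the early times: "Blood samples for PK will be collected at 15 min, 30 min, 45 min, 1h, 3h, 6h, and 12h postdose". SAP 4.3.1.1 adds 24, 36, 48 and 72 h, with full profiles "drawn on Day 1 and Day 29 at the following nominal time points".

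On kinetics, protocol 1.2.2 reports a median tmax "of about 0.5-1.0h" and says "The apparent terminal half-life was 2 to 4h in the dose range tested". SAP 1.1.1 says "The mean terminal apparent half-life ranged between 2 and 8 hours". Protocol 1.1.2 describes "a rapid and large elimination phase and a slower and low distribution phase", and protocol 1.2.2 adds that "ELX-02 was excreted and recovered almost quantitatively in the urine during the first 12 hours". Neither document gives an LLOQ or a half-life by dose.

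**The concern.** At half-lives of 2-4 h, the 6-12 h gap spans 1.5 to 3 half-lives and the 12-24 h gap spans 3 to 6. Exponential decline is convex, so the chord between two samples lies above the curve. In the decline the direction of the error is therefore known in advance, and adding subjects does not reduce it.

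Blood and urine PK parameters are a primary endpoint (protocol 2.2.1). The absolute AUC, CL/F, Vd/F and renal clearance from this study are values that later work would carry forward. AUCt and AUCinf also feed the proportionality slope (SAP 4.3.2), so it matters whether the error is the same at every dose.

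**Working it through.** The documents give no figure for the integration error, so there is none of theirs to reproduce.

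**Model.** One compartment with first-order absorption, ka = 4/h (assumed). This puts tmax at 0.67 to 0.98 h over half-lives of 2 to 8 h, inside the protocol's range. Scaled so that the true AUCinf is 1/ke:

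C(t) = ka/(ka − ke) × (e^(−ke·t) − e^(−ka·t)), with ke = ln 2 / t½.

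Sampling times are 0, 0.25, 0.5, 0.75, 1, 3, 6, 12, 24, 36, 48 and 72 h, all quantifiable.

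**Worked case, t½ = 3 h.** ke = 0.2310, true AUCinf = 4.328, C(6) = 0.2653, C(12) = 0.0663, C(24) = 0.0041.

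- 6-12 h: linear (0.2653 + 0.0663)/2 × 6 = 0.995; exact 0.861; excess 3.1% of total AUC.
- 12-24 h: linear (0.0663 + 0.0041)/2 × 12 = 0.423; exact 0.269; excess 3.6%.
- 3-6 h: linear 1.194; exact 1.148; excess 1.1%.
- All other segments together: about −0.05%, mainly a small undershoot during absorption.
- Total: linear AUCinf 4.660/4.328 = 1.077.

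**By half-life** (CL/F error = 1/ratio − 1):

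| t½ (h) | Linear AUCinf error | CL/F error | Linear-up/log-down AUCinf error |
|---|---|---|---|
| 2 | +8.5% | −7.8% | −1.1% |
| 3 | +7.7% | −7.1% | −0.8% |
| 4 | +6.7% | −6.3% | −0.6% |
| 8 | +3.9% | −3.8% | −0.3% |

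At 2-4 h, the 6-12 h and 12-24 h segments alone contribute 6.0 to 6.6 points. With λz correct, Vd/F is off by the same factor as CL/F. Renal clearance is off by almost the same factor, because AUC72h has nearly the same error as AUCinf.

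**Other shapes.** I also tried bi-exponential decline with assumed fast half-life 1-2 h, slow half-life 4-8 h and 2-20% of AUC in the slow phase. The linear error is about +8% to +11% if the LLOQ is 0.01% of Cmax, and about +1% to +8% if it is 1% of Cmax. A single 8 h half-life would eliminate only 1 − 2^(−12/8) = 65% by 12 h, against 88% at 4 h and 98% at 2 h. That sits poorly with near-complete urinary recovery by 12 h, so the 4% end is the less plausible one.

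**Dose dependence.** Post-peak BLQ values are treated as missing (SAP 4.3.1.2), so the last usable time can lengthen with dose. With an assumed LLOQ of 1/500 of the 5 mg/kg Cmax and t½ = 3 h at all doses:

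| Dose (mg/kg) | 0.1 | 0.3 | 1.0 | 2.5 | 5.0 |
|---|---|---|---|---|---|
| Last usable sample (h) | 6 | 12 | 12 | 24 | 24 |
| Linear AUCinf error | +0.8% | +3.9% | +3.9% | +7.4% | +7.4% |

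The entry at 0.1 mg/kg uses the true λz; with λz fitted to the last three points it is +1.3%. With 6, 6, 12, 12 and 6 active subjects, the slope β moves by about 0.016 (fitted λz) to 0.017 (true λz). With equal half-life across doses it moves by up to about 0.011 at an LLOQ of 1/2000, and by 0.001 to 0.008 at 1/10000. With log-down and equal half-life it does not move.

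**Scale.** The 90% CI half-width for β is t × s/√Sxx, with t = 1.684 (40 df), Sxx = 66.1 and s = √ln(1 + CV²). An assumed CV of 15% gives 1.684 × 0.149/8.13 = 0.031; 30% gives 1.684 × 0.294/8.13 = 0.061.

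**The case against.** The strongest case for leaving the plan alone has four parts.

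- **The rule is prespecified and consistent.** Protocol and SAP agree, apply it on both days, and leave no ambiguity. This stands: the point is a better method, not an inconsistency.
- **The comparisons are largely protected.** With similar half-life and last usable time, the bias cancels in the accumulation ratios and in the 50 versus 100 mg/mL comparisons. SAP 4.3.2 sets no acceptance limit for β. This stands too.
- **The worst dose pattern is partly screened out.** In the 0.1 mg/kg case above, about 26-27% of AUCinf is extrapolated. SAP 4.3.1.2 drops AUCinf from summary statistics when extrapolation exceeds 20%. Excluding it narrows the summarised spread to +3.9% to +7.4%. The rule does not explicitly cover the regression.
- **The change would be late.** All seven cohorts had been investigated when the SAP was written (SAP 1.2.1), and the pharmacokineticists see individual concentrations before lock (SAP 1.2.4). Replacing the rule at that stage needs safeguards, which is why the linear results must still be reported in full.

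A reader might infer that the error differs across doses and so distorts the proportionality assessment. The documents do not support stating that as fact: it needs an LLOQ and dose-specific half-lives, and neither is given. With a sensitive assay and a common half-life, the error is nearly constant and largely cancels in β.

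**Conclusion.** The upward bias in absolute AUC holds, with matching downward bias in CL/F, Vd/F and renal clearance. It is about 7-8% at the protocol's 2-4 h half-life and about 4% at 8 h, assuming one compartment, ka near 4/h and all samples quantifiable. It is smaller if late samples are lost and up to about 11% in some bi-exponential cases. The CL/F part also assumes Dose/AUCinf.

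The effect on proportionality is conditional and small. The largest shift found, about 0.016 to 0.017 in β, requires a coarse assumed LLOQ and lies inside the likely confidence interval. For comparison, the 24-fold AUC rise over a 25-fold dose range in the single-dose studies is a slope of ln 24/ln 25 = 0.987, a departure of 0.013. A change in the proportionality conclusion is unlikely.

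This is a low-severity, worthwhile improvement. The 2-4 h and 2-8 h half-life statements should also be reconciled, because the size of the bias depends on them.

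**What to change.** Compute AUCt, the partial AUCs, AUCinf and everything derived from them (CL/F, Vd/F, renal clearance, AUC accumulation ratio, β) by linear-up/log-down in Phoenix. Record the change and its reason in SAP Section 5, state the CL/F formula, and report the prespecified linear-rule results in full beside the new ones.

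If the sponsor prefers to keep the linear rule as primary to preserve prespecification, add linear-up/log-down AUC, CL/F, Vd/F, renal clearance and β as a sensitivity table. That also resolves the point.

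The cost is a software setting and one extra set of tables, with no new samples or visits. The downside is a departure from the protocol's rule after cohorts have been run, and possibly from the method of the single-dose studies. Side-by-side reporting covers both.
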